2.1 Secondary Endpoints

Secondary endpoints will consist of the following with level of analysis in parentheses:

- 1) Change in percent stenosis after treatment with RevolutionTM Peripheral Atherectomy System, determined after atherectomy and prior to other adjunctive therapies, as measured by the angiographic core laboratory (lesion level);
- 2) Procedural success as defined by target lesion residual stenosis of $<30\%$ at the conclusion of the index procedure, after atherectomy and any adjunctive endovascular treatment, as measured by the angiographic core laboratory (lesion level);
- 3) Assessment of the individual components of the primary safety endpoint (MAE); including all-cause mortality, major target limb amputation, clinically significant distal embolization, major target vessel perforation requiring surgical or endovascular repair, and clinically-driven TLR, measure through 30 days and at 6 months (subject level);
- 4) Minor unplanned target limb amputation rate through 30 days and 6 months (subject level);
- 5) Myocardial infarction through 30 days and 6 months (subject level);

³ The shoulder-to-shoulder length is determined visually using a Quantitative Vascular Angiography (QVA) software application. RVD is determined at the location of the MLD, linearly interpolated between the luminal diameters just proximal to and distal to each shoulder.

- 6) Incidence of target vessel revascularization (TVR) through 30 days and 6 months (subject level);
- 7) Frequency of angiographic procedural distal embolization (symptomatic) in the target limb as confirmed angiographically by the core laboratory (subject level);
- 8) Primary patency of the target lesion at 30 days and 6 months, determined by duplex ultrasound or angiography (subject level);
- 9) Primary-assisted patency of the target lesion at 30 days and 6 months, determined by duplex ultrasound or angiography (subject level);
- 10) Secondary patency of the target lesion at 30 days and 6 months, determined by duplex ultrasound or angiography (subject level).

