3.3 Sample Size Consideration

This study will enroll up to 121 subjects at up to 18 investigational sites and the sample size estimation was based on binomial hypothesis testing of a single proportion.

The performance goal (PG) of 80% has been established for the primary safety endpoint. Sample size estimation was based on a one-sided 97.5% exact binomial test. The 30-day

⁴ This point is defined as entry of the study device into the access sheath/guide at the level where the sheath/guide enters the subject's body.

MAE rate is anticipated to be approximately 9%. Under these assumptions, the required sample size to achieve a level of 90% power is 110 subjects (Table 1). Assuming 10% attrition over 30 days, initial enrollment of 121 subjects is necessary.

A PG of 76% has been established for the primary effectiveness endpoint. Anticipating an actual technical success rate of approximately 86%, and based upon a one-sided 97.5% exact binomial test, the required sample size to achieve a level of 90% power is 165 target lesions. Assuming a 1.5 ratio of subjects to treated target lesions, approximately 110 subjects will be necessary (Table 2). Since the primary effectiveness endpoint is determined at the time of the index procedure, no attrition has been taken into account.

Table 1. Sample Size – Primary Safety Endpoint

Primary Safety Endpoint	
Performance goal	80%
Anticipated freedom from MAE	91%
Significance level	.025
Statistical test	One-sided exact binomial test
Desired power level	90%
Required sample size prior to attrition (subjects) adjustment*	110
Required sample size after attrition rate adjustment	121
*Assumes 10% 30-day attrition	

Table 2. Sample Size – Primary Effectiveness Endpoint

Primary Effectiveness Endpoint	
Performance Goal	76%
Anticipated technical success rate	86%
Significance level	.025
Statistical test	One-sided exact binomial test
Desired power level	90%
Required sample size (target lesions)	165
Estimated subjects required for required number target lesions*	110
*Assumes 1.5 target lesions treated/subject; ratio calculated from atherectomy literature review.	

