Step 2. If the scheduled assessment is not completed or is not evaluable (i.e. not readable or non-diagnostic), this assessment will be censored (or excluded from proceeding to the next step).

Step 3. If a visit has multiple DUS or angiographic assessments, the following hierarchical criteria will be used to identify the appropriate assessment for that visit:

- Choose the one that has a positive observation(s) – i.e. significant reduction of blood flow, etc.; if more than one assessment contains at least one positive observation, the earliest assessment will be used;
- If none of the assessments has positive observations, choose the one that is the closest to the scheduled visit date

Step 4. If a visit has both DUS assessment and angiographic assessment, the following hierarchical criteria will be used to identify the appropriate assessment for that visit to use in the analysis:

- If there are multiple DUS assessments or multiple angiographic assessments that are slotted in the same visit window, please refer to step 3 to select one non-missing assessment for DUS and/or angiography separately. Please refer to the following table for the assessment and outcome determination

DUS assessment	Angiographic assessment	Final selected assessment	Final selected assessment outcome
Success	Failure	Angiography	Failure

Success	Success	Choose the one that is the closest to or earlier than the scheduled visit date	Success
Success	Missing	DUS	Success
Failure	Failure	Choose the one that is the closest to or earlier than the scheduled visit date	Failure
Failure	Success	Angiography	Success
Failure	Missing	DUS	Failure
Missing	Failure	Angiography	Failure
Missing	Success	Angiography	Success
Missing	Missing	N/A	Missing

As stated previously and shown in the hierarchy above, in cases where both angiography and DUS are available at the same assessment and they provide different conclusions then angiography will be preferentially used.

The step-by-step description of the above hierarchical criteria in determining the 1 and 6-month site assessments is as follows:

- 1) Remove the assessments with value of 'N/A' or 'missing'. If the assessment result is N/A or missing, then delete (e.g., set the value to 'missing');

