5.21 Primary Patency

Censor any DUS or angiogram assessments taken after any TVR as a revascularization changes the vessel making it unevaluable. If the date of assessment > date of TVR, then delete (e.g., set the value to 'missing').

At the time of a CD TLR set primary patency to failure.

Once a failure of primary patency has occurred in a subject all future time points reporting primary patency will be set to failure. If there are no failures and one or more successes, then the subject is a success up to the time of the last success recorded.

Unique composite endpoint such as primary patency contains both site-reported imaging endpoint and clinical/safety endpoint (by cut-off days), the event of the

individual components will be determined first, and the composite endpoint will then be determined as the following:

Freedom from significant stenosis/occlusion within 1-Month	Freedom from CD TLR within 37 Days	1-Month Primary Patency
Yes	Yes	Yes
Yes	No	No
Yes	Missing Data	Missing Data
No	Yes	No
No	No	No
No	Missing Data	No
Missing Data	Yes	Missing Data
Missing Data	No	No
Missing Data	Missing Data	Missing Data

Primary Patency at 6 months follow-up will be determined following similar convention specified above for 1 month.

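### Subject-level patency rules do not link imaging, TVR or TLR to a target lesion, so subjects with several lesions can be scored in contradictory or wrong ways

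*SAP*

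**What the plan says.** SAP 2.1 Secondary Endpoints, item 8, reads "Primary patency of the target lesion at 30 days and 6 months, determined by duplex ultrasound or angiography (subject level"). Items 9 and 10 (primary-assisted and secondary patency) carry the same label. Technical success and secondary items 1 and 2 are lesion level.

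Several lesions per subject are expected. The footnote to SAP Table 2 says "Assumes 1.5 target lesions treated/subject; ratio calculated from atherectomy literature review". Protocol 6.3 allows several target lesions in one limb, in the superficial femoral (SFA), popliteal or tibial arteries.

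The scoring rules work by subject and visit:

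- **SAP 5.2, Step 3.** Among several scans of one modality at a visit: "Choose the one that has a positive observation(s").
- **SAP 5.2, Step 4 table.** If duplex and angiography disagree, angiography decides. Duplex failure with angiographic success is scored as success.
- **SAP 5.2, step-by-step description after Step 4, item 2.** Take the first angiographic failure; if there is none, take the first duplex failure; use successes only if there is no failure of either kind.
- **SAP 5.21.** "Censor any DUS or angiogram assessments taken after any TVR as a revascularization changes the vessel making it unevaluable". A CD TLR makes primary patency a failure, and "Once a failure of primary patency has occurred in a subject all future time points reporting primary patency will be set to failure".
- **SAP 5.22 and 5.23.** Primary-assisted and secondary patency fail on a second CD TLR, with no statement that it must be on the same lesion.

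The only multi-lesion rule for subject-level effectiveness endpoints is in SAP 4.3. It excludes subjects who have a lesion outside the per-protocol set. It does not say how the qualifying lesions of one subject combine.

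**The concern.** The thing measured is a lesion and the thing reported is a subject, and the step between them is missing. With one target lesion this does no harm. With two, a programmer following the text has no key that says which lesion a scan or a revascularization belongs to.

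The reasons given for two of the rules also hold only within one vessel. Angiography is preferred because it shows the vessel more precisely, which is no ground for letting a picture of one lesion overrule a picture of another. Scans after a TVR are discarded because the vessel has been altered, which is not true of a lesion in a different artery.

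At stake is whether the three patency figures have a defined meaning. The descriptive subgroups by SFA, popliteal and tibial artery (Protocol 7.11, SAP 4.64) are also affected. A subject with an SFA and a tibial lesion has one patency result and no rule for assigning it to an artery.

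**Working it through.** **1. The plan's own figure.** SAP 3.3 states that "the required sample size to achieve a level of 90% power is 165 target lesions", and then: "Assuming a 1.5 ratio of subjects to treated target lesions, approximately 110 subjects will be necessary (Table 2"). The figure reproduces as 165 / 1.5 = 110. That sentence words the ratio the other way round, but only the reading in the Table 2 footnote (lesions per subject) gives 110.

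**2. How many subjects have more than one lesion.** Protocol 7.3 originally planned a method for clusters of one or two lesions. With at most two each and a share f having two: (1 − f) × 1 + f × 2 = 1.5, so f = 0.5, and 0.5 × 110 = 55 subjects. If three are possible, 75% with one and 25% with three also average 1.5 (0.75 × 1 + 0.25 × 3), giving 27.5 of 110. The documents do not give the distribution.

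**3. The rules applied to a subject with lesions A and B in different vessels.**

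| Case | Result under the text | Result if each lesion were scored and all had to be patent |
|---|---|---|
| (1) A fails on duplex; B succeeds on angiography in the same window | Step 4 table: success. Step-by-step item 2: no angiographic failure, so the duplex failure is taken: failure | Failure |
| (2) TVR in A's vessel without a CD TLR and with no earlier imaging failure; B fails on a later scan | 5.21 deletes B's scan. The result is missing, or success if an earlier successful scan lies in the same analysis window | Failure |
| (3) First CD TLR on A for stenosis, then first CD TLR on B for stenosis; both patent afterwards | 5.22 can be read as a second CD TLR in the subject: assisted-patency failure. 5.23 has the same gap for occlusions | Success |

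Case (1) is a contradiction between two parts of SAP 5.2. Cases (2) and (3) come from the missing lesion link.

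The condition in case (2) matters. If the TVR included a CD TLR, or if imaging had already failed, 5.21 has already set primary patency to failure and carries it forward. Deleting later scans then changes nothing at subject level.

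**4. A ceiling for case (1).** It can arise only where one lesion is patent and the other has failed. For two-lesion subjects with lesion patency p and within-subject correlation ρ, the discordant probability is 2p(1 − p)(1 − ρ). Neither p nor ρ is in the documents; SAP 4.3 says the correlation is unavailable. Both are therefore assumed:

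- p = 0.80, ρ = 0: 2 × 0.80 × 0.20 × 1 × 55 = 17.6 subjects
- p = 0.80, ρ = 0.3: 0.32 × 0.7 × 55 = 12.3 subjects
- p = 0.80, ρ = 0.5: 0.32 × 0.5 × 55 = 8.8 subjects
- Over p from 0.70 to 0.95 and ρ from 0 to 0.5: 23.1 (p = 0.70, ρ = 0) down to 2.6 (p = 0.95, ρ = 0.5)
- ρ = 1: none

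Only those discordant subjects who have a duplex of the failed lesion and an angiogram of the patent one in the same window are affected. The documents give no frequency for that, and no TVR or TLR rates from which to count cases (2) and (3).

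**5. What is not touched.** Technical success is scored per lesion, MAE is scored per subject, and the success criteria in SAP 4.5 use only those two. No patency endpoint has a performance goal or a hypothesis test.

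**The case against.** The strongest reply is that subject level is a declared choice. SAP 2.1 gives a level for every secondary endpoint, and SAP 4.3 treats lesion-level and subject-level effectiveness endpoints differently. A subject endpoint that fails when any lesion fails is legitimate, and Step 3 with the first-failure rule largely behaves like one. **This stands.** A reader might infer that subject-level scoring biases patency downward. The documents do not support that: lesion patency and all-lesions-patent are different estimands, and the gap between them at an assumed rate is not an error.

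A reader might also infer that case (1) inflates patency. It would under the Step 4 table, but the step-by-step item gives failure, so the direction is not established. The same conflict arises with a single lesion. There, however, the SAP says twice that angiography prevails, whereas with two lesions that reason does not apply. The case also needs both modalities in one window. Follow-up imaging is duplex or angiography, and all target lesions are in one limb, so one examination may cover both. Unscheduled scans do count, though, and the analysis windows are wide (days 15 to 60 and 61 to 210), so the case is possible.

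Third, the CRF is not shown and may record imaging by lesion. That is fair, but the SAP does not tell the programmer to use such records.

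Finally, it is tempting to say that acute and follow-up results cannot be compared. No such comparison is planned, and the acute endpoints, which are lesion level, can be split by artery without difficulty.

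**Conclusion.** The point holds as a defect in the scoring rules, not in the choice of subject level. For subjects with several target lesions, the text gives contradictory results in case (1). In case (2) it can lose a genuine failure when no imaging failure or CD TLR came before. In case (3) it can count two first TLRs as a second one. Each departs even from a plain rule that all target lesions must be patent.

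The exposed group is about half of subjects, assuming at most two lesions each. The number actually misclassified cannot be derived from the documents; the counts in the working are ceilings for case (1) at assumed patency and correlation. The consequence is limited to three secondary endpoints with no performance goal and to their descriptive artery subgroups. Neither the primary endpoints nor the sample size is affected. It should be settled before the patency analyses are run, because the choice could otherwise be made with results in view.

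**What to change.** In SAP 5.2 to 5.23:

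1. Apply Steps 1 to 4 and the three patency algorithms to each target lesion. Angiography then supersedes duplex only for the same lesion, and failure is carried forward by lesion.
2. In 5.21, censor scans only after revascularization of the vessel that contains that lesion.
3. In 5.22 and 5.23, define the second CD TLR as one on the same lesion.
4. Reconcile the Step 4 table with the step-by-step description, so that duplex failure with angiographic success of the same lesion has one result.
5. State the combination rule: a subject is patent only if all target lesions are patent. This keeps the declared subject level.

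Where per-lesion records exist, also report lesion-level patency, allowing for clustering within subject, as a supportive figure and as the basis for the SFA, popliteal and tibial subgroups. Making lesion level the main analysis is a trade-off for the sponsor and is not needed to repair the rules.

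The cost is tabulating imaging and revascularization records by lesion or vessel, plus some extra programming. The scans are already scheduled. Whether site duplex reports separate two lesions in the same vessel cannot be seen from the documents and should be checked first.

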3. ANALYSIS POPULATION

The point of enrollment in this study occurs when a study device first enters a subject's vasculature.⁴ The following populations will be analyzed in the study:

3.1 Intention-To-Treat (ITT) Analysis

The ITT analysis will be performed on all enrolled subjects in whom the study device entered the vasculature, irrespective of adherence with the entry criteria, treatment actually received, subsequent withdrawal, or deviation from the investigational plan. Analysis of safety outcomes will use the ITT population.

3.2 Per Protocol (PP) Analysis

The PP analysis will be performed on target lesions with core laboratory determined RVD falling within the pre-specified anatomic eligibility criteria of ≤ 4.0 mm. The effectiveness endpoints will be determined using the PP analytic subset to exclude lesions where the largest bore (2.0 mm) study device is less than 50% of the RVD. The per protocol population has no other pre-specified inclusion/exclusion violations(s) or requirement for adequate follow-up (or a loss of patency).

3.3 Sample Size Consideration

This study will enroll up to 121 subjects at up to 18 investigational sites and the sample size estimation was based on binomial hypothesis testing of a single proportion.

The performance goal (PG) of 80% has been established for the primary safety endpoint. Sample size estimation was based on a one-sided 97.5% exact binomial test. The 30-day

⁴ This point is defined as entry of the study device into the access sheath/guide at the level where the sheath/guide enters the subject's body.

MAE rate is anticipated to be approximately 9%. Under these assumptions, the required sample size to achieve a level of 90% power is 110 subjects (Table 1). Assuming 10% attrition over 30 days, initial enrollment of 121 subjects is necessary.

A PG of 76% has been established for the primary effectiveness endpoint. Anticipating an actual technical success rate of approximately 86%, and based upon a one-sided 97.5% exact binomial test, the required sample size to achieve a level of 90% power is 165 target lesions. Assuming a 1.5 ratio of subjects to treated target lesions, approximately 110 subjects will be necessary (Table 2). Since the primary effectiveness endpoint is determined at the time of the index procedure, no attrition has been taken into account.

Table 1. Sample Size – Primary Safety Endpoint

Primary Safety Endpoint	
Performance goal	80%
Anticipated freedom from MAE	91%
Significance level	.025
Statistical test	One-sided exact binomial test
Desired power level	90%
Required sample size prior to attrition (subjects) adjustment*	110
Required sample size after attrition rate adjustment	121
*Assumes 10% 30-day attrition	

Table 2. Sample Size – Primary Effectiveness Endpoint

Primary Effectiveness Endpoint	
Performance Goal	76%
Anticipated technical success rate	86%
Significance level	.025
Statistical test	One-sided exact binomial test
Desired power level	90%
Required sample size (target lesions)	165
Estimated subjects required for required number target lesions*	110
*Assumes 1.5 target lesions treated/subject; ratio calculated from atherectomy literature review.	

4. STATISTICAL METHODS OF ANALYSIS

4.1 Statistical Methodology

The objective of the statistical design for this study is to evaluate the safety and effectiveness of the study device, as assessed in comparison to literature-derived performance goals.

The safety and effectiveness performance goals were determined from a literature review of atherectomy publications. A total of 19 studies were included in this review and, among these, 13 reported data referable to the primary safety endpoint and 7 reported data referable to the primary effectiveness endpoint. Studies with populations that overlapped the population of another study were excluded. See the study protocol for more details on the results of the literature review on primary safety and effectiveness endpoints.

4.2 Baseline Comparability

Poolability of data across clinical study sites is justified on a clinical basis (i.e. all study sites use the same protocol) the sponsor monitors the site for protocol compliance, and the data gathering instruments are identical. The Food and Drug Administration (FDA) also requires a statistical assessment of poolability. This is done by comparing the baseline characteristics across study sites. For categorical baseline variables, such as sex, a generalized Fisher's exact test or equivalent test will be used and for quantitative variables, parametric or non-parametric analysis of variance (general linear models or an equivalent procedure) will be used.

The above statistical analyses do not result in an impediment to pooling, but rather assess the balance of baseline covariates across study sites. If any baseline covariate is found to be statistically significant by this process, multivariate analyses will be done to determine if imbalance affected study outcome. This is done by using both the variable found out of balance and study site as possible covariates.

It may be necessary to combine two or more low enrolling study sites into pseudo-sites to allow these analyses. Sites with fewer than 6 subjects will be ranked by enrollment low to high. Starting from the lowest enrollment sites, sites will be combined into a pseudo sites until the combined size reaches the median enrollment among all sites. This process will be repeated until all resulting sites have enrollment equal to or greater than 6 subjects. This will be done in a manner to preserve the structure of the study and prevents bias.

Baseline characteristics to be considered as possible covariates are as following:

- Age
- Sex
- Coronary artery disease
- Chronic obstructive pulmonary disease
- Myocardial infarction
- Hyperlipidemia
- Cerebrovascular accident
- Hypertension
- Diabetes
- History of tobacco use
- History of peripheral vascular disease
- Rutherford Category
- ABI/TBI

If there are relatively few missing data points (e.g., <10%) for a given variable, a simple sex-specific imputation using the mean (for continuous variables) or median (for dichotomous or categorical variables) of the non-missing values will be done. If there are >10% missing, the variable will be excluded from the imputation analysis.

Poolability analysis will also be performed on the primary endpoints comparing across sites after adjusting for covariates difference. Logistic regression models will be utilized to include unbalanced covariates and site as an independent variable and the study outcome as dependent variable to assess outcome difference. If the p-value of site effect is less than 0.10, further analyses will be undertaken to investigate the imbalance of the study outcome.

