	
atherectomy and any adjunctive endovascular treatment, as measured by the angiographic core laboratory.
 
3. Assessment of the individual components of the primary safety endpoint (MAE); including all-cause mortality, major target limb amputation, clinically significant distal embolization, major target vessel perforation requiring surgical or endovascular repair, and clinically-driven TLR, measured through 30 days and at 6 months.4. Minor unplanned target limb amputation rate through 30 days and 6 months;5. Myocardial infarction through 30 days and 6 months;6. Incidence of target vessel revascularization (TVR) through 30 days and 6 months;7. Frequency of angiographic procedural distal embolization (symptomatic) in the target limb as confirmed angiographically by the core laboratory;8. Primary patency of the target lesion at 30 days and 6 months, determined by duplex ultrasound or angiography;9. Primary-assisted patency of the target lesion at 30 days and 6 months, determined by duplex ultrasound or angiography;10. Secondary patency of the target lesion at 30 days and 6 months, determined by duplex ultrasound or angiography.
Patient Population	Subjects with symptomatic PAD eligible for treatment with the Revolution™ Peripheral Atherectomy System with atherosclerotic lesions of the superficial femoral, popliteal and tibial arteries will be eligible for inclusion in the study.
Inclusion Criteria	Subjects must meet the following criteria to be included in the study: 
1. Age \geq 18 years;2. Willing and able to provide informed consent;3. Ability to take at least one form of anti-platelet therapy.4. Rutherford Categories 2, 3 or 4 in the target limb; Rutherford category 5 if no exposed bone, tendon or active infection;5. Lesions to be treated with the study device must be located in the same limb;6. Target lesion(s) located within the superficial femoral, popliteal or tibial arteries;7. Target lesion(s) with stenosis $\geq 70\%$ diameter reduction as measured by site-reported angiography;8. Target lesion length(s) ≤ 150 mm;

	
9. Target lesions(s) with reference vessel diameter (proximal and distal to target lesion) ≥ 2.0 mm and ≤ 4.0 mm.

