Analytical Sets	The regulatory submission will be based on an approximate sample size of 121 subjects. Assuming a lesion-to-subject ratio of 1.5, approximately 165 target lesions will be evaluable for the primary effectiveness endpoint. Subset analyses will be performed for device effectiveness for superficial femoral/popliteal and tibial artery target lesions.
Pre-Enrollment Testing	Medical history, physical examination with vital signs and directed peripheral vascular examination, laboratory assessment, ankle-brachial or toe-brachial index, and patient-reported outcome measures. The diagnostic angiogram at time of the planned index procedure is performed prior to the point of enrollment in the study; eligibility is, in part, based upon the anatomic findings of the angiogram.
Follow-Up Schedule	Subjects will have required follow-up evaluations at the following time points: 
1. Discharge;2. 1 month post index procedure;3. 6 months post index procedure;
Follow-Up Data Collection	
1. Adverse Events at the index procedure, hospital discharge, and through 6 months;2. Rutherford Category at 1 and 6 months;3. Ankle-brachial or toe-brachial index at 1 and 6 months;4. Duplex ultrasound or angiography of the target vessel at 1 and 6 months.
Clinical Events Committee (CEC)	An independent CEC will review all primary safety endpoint events, unanticipated adverse device effects, and other important safety occurrences as specified in the CEC Charter.
Data Safety Monitoring Board (DSMB)	An independent Data Safety Monitoring Board (DSMB) will review safety data from the study at predetermined time points and as deemed necessary by the Sponsor or the DSMB Chair. The DSMB will make recommendations on protocol modifications and continuation of the study.
Principal Investigator	[name], MD

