6.3. Inclusion Criteria

Subjects may be enrolled in the study if they meet the following criteria:

1. Age \geq 18 years;
2. Willing and able to provide informed consent;
3. Ability to take at least one form of anti-platelet therapy;
4. Rutherford categories 2, 3, or 4 in the target limb; Rutherford category 5 if no exposed bone, tendon or active infection;
5. Lesions to be treated with the study device must be located in the same limb;
6. Target lesion(s) located within the superficial femoral, popliteal or tibial arteries;
7. Target lesion(s) with stenosis $\geq 70\%$ diameter reduction as measured by site-reported angiography;
8. Target lesion length(s) ≤ 150 mm;
9. Target lesions(s) with reference vessel diameter (proximal and distal to target lesion) ≥ 2.0 mm and ≤ 4.0 mm.

A subject must have at least one target lesion that meets the anatomic inclusion criteria above. Other lesions that do not meet these criteria may be treated but must not be treated with the study device and will not be considered target lesions. Bilateral treatment with the study device is not permitted.

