2.2 Primary Effectiveness Endpoint

The primary effectiveness endpoint is technical success defined as acute debulking resulting in a reduction of stenosis to $\leq 50\%$ after treatment with RevolutionTM Peripheral Atherectomy System from baseline and prior to other adjunctive therapies at the conclusion of the index procedure, as measured by angiographic core laboratory.

Within any target lesion, stenosis is measured at the point of the minimum luminal diameter (MLD) over its shoulder -to – shoulder length³. The reference vessel diameter (RVD) is the interpolated diameter from the point just proximal to the point just distal to the target lesion. The percent stenosis is calculated as:

$$\% \text{ Diameter Stenosis} = 1 - \text{MLD}/\text{RVD}.$$

This is a lesion level endpoint.

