4.64 Subgroup Analyses

Subgroup analyses will be performed on target lesions of the superficial femoral, popliteal and tibial arteries. Additional subgroup analyses are planned for gender, diabetes mellitus, Rutherford Class, Age 75 years cutoff, lesion length tercile, and chronic total occlusion. The analyses will comprise descriptive analyses of the primary and secondary effectiveness endpoints.

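### The poolability covariate list contains no lesion characteristics, so the site test on technical success cannot separate a site effect from lesion difficulty if lesion mix differs between sites

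*SAP*

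**What the plan says.** SAP 4.2 compares baseline characteristics across sites and then tests for a site effect on the primary endpoints. The list opens with "Baseline characteristics to be considered as possible covariates are as following" and has 13 entries: age, sex, nine history or comorbidity items (one of them "History of peripheral vascular disease"), Rutherford category, and ABI/TBI as a single entry. Protocol 7.14 has the same list.

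For the outcome comparison, "Logistic regression models will be utilized to include unbalanced covariates and site as an independent variable and the study outcome as dependent variable". A site p-value below 0.10 leads to further analyses. The plan also says that the baseline comparison does not stand in the way of pooling.

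On technical success, SAP 2.2 states: "This is a lesion level endpoint". Lesions may differ widely. Protocol 6.3 admits "Target lesion(s) located within the superficial femoral, popliteal or tibial arteries", up to 150 mm long, with RVD from 2.0 to 4.0 mm.

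Anatomy does appear elsewhere in the SAP. Section 4.61 describes it at baseline. Section 4.64 plans descriptive subgroups by vessel and adds: "Additional subgroup analyses are planned for gender, diabetes mellitus, Rutherford Class, Age 75 years cutoff, lesion length tercile, and chronic total occlusion". Section 4.65 plans predictor models without naming the predictors. None of these is tied to the site comparison.

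**The concern.** The site test asks whether technical success differs between sites beyond what the patients' characteristics explain. Technical success is a core-laboratory measurement on one lesion, so the characteristics most likely to explain it are those of the lesion. None is on the list. However unequal the lesions are between sites, the screen will not see it and the model will not adjust for it.

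A site that treats larger vessels or more occlusions could then be flagged for its case mix. Conversely, a real site effect could be hidden by an easier mix. At stake is how the poolability check reads, which the SAP says FDA requires.

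A smaller point concerns ABI/TBI. Either index is accepted at baseline (Protocol synopsis, pre-enrollment testing: "laboratory assessment, ankle-brachial or toe-brachial index, and patient-reported outcome measures"), and the plan gives no rule for coding the shared entry.

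**Working it through.** **1. The sample available to the site model.** Inputs from SAP 3.3: performance goal 76%, expected success 86%, one-sided 0.025, power 90%. By the normal approximation:

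n = [(1.960·√(0.76·0.24) + 1.2816·√(0.86·0.14)) / 0.10]² = 164.3, rounded up to 165.

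This equals the plan's 165 lesions. Exact binomial power at 165 (success at 137 or more) is 88.5%. Expected failures are 165 × 0.14 = 23.1. With 121 subjects at up to 18 sites, the mean is 121/18 = 6.7 subjects per site.

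**2. Is any lesion variable known to drive success?** RVD is, by the plan's own argument. Protocol 6.5 (footnote), Protocol 7.3 and SAP 4.3 exclude RVD above 4.0 mm because a 2 mm bit cannot then leave a channel of half the vessel. Apply the same premise (channel = bit diameter) to the ranges in Protocol Table 1, with % stenosis = 1 − MLD/RVD:

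| Bit (mm) | RVD range (mm) | Residual stenosis at low end | At high end |
|---|---|---|---|
| 1.33 | 2.00–2.49 | 33.5% | 46.6% |
| 1.66 | 2.50–2.99 | 33.6% | 44.5% |
| 2.00 | 3.00–4.00 | 33.3% | 50.0% |

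With the 2.00 mm bit, the margin to the 50% criterion shrinks from 16.7 points to zero inside the eligible range.

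**3. What omission could do to the site test.** The documents give no lesion mix by site and no success rate by lesion type, so these are assumed values. Setting: 8 pseudo-sites, 165 independent lesions, 86% success overall, no true site effect, likelihood-ratio logistic test at p<0.10, 1,500 runs, one binary lesion covariate (easy or hard).

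| Share of hard lesions across sites | Success, easy / hard | Site p<0.10, covariate omitted | Covariate included |
|---|---|---|---|
| 30% at every site | 90% / 76.7% | 16% | 16% |
| 10% to 50% | 90% / 76.7% | 19% | 17% |
| 10% to 50% | 95% / 65% | 31% | 16% |
| 0% to 80% | 95% / 72.5% | 51% | 15% |

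Each row averages 86%; for example, 0.7 × 95 + 0.3 × 65 = 86.0. The floor of 15% to 17%, above the nominal 10%, reflects sparse failures.

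**4. How many terms the model can carry.** Vessel (2 df), length, occlusion, baseline stenosis and RVD make 6 df. With six uninformative df forced in and no site effect, false site signals rose from 18.1% to 22.1% with 12 sites and from 20.2% to 26.4% with 18. Entering a lesion covariate only when it is unbalanced avoids most of that. In a further run with assumed values, the screened rule cut false signals from 17–27% to 7–12% when mix differed strongly, and changed nothing when it did not. That run's set-up differs from the table's, so only the direction should be compared.

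**5. ABI/TBI.** Assume 12 sites of 10, ABI mean 0.70 (SD 0.20), TBI mean 0.45 (SD 0.15), raw values pooled, and no true difference. If two whole sites use TBI, the pooled variable is flagged at p<0.05 in 97.5% of trials. With 25% of subjects having TBI scattered across sites, the rate is 5.0%, which is nominal.

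**The case against.** The strongest reply is that nothing decisive depends on this check. Study success (SAP 4.5) is a lower confidence limit against 76%, with no covariate adjustment stated. A site p-value below 0.10 only opens further analyses, in which case mix could be examined. Anatomy is also described at baseline and used in subgroups, and the predictor models leave their covariates open. All of this stands, and it limits the point to a supportive analysis. It does not put any lesion variable into the site model.

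A reader might go further and infer that site effects on technical success will be mis-adjusted. The documents do not show that. It requires lesion mix to differ by site and also to predict success, and the first row of the simulation shows no harm when mix is equal. Subject-level covariates in a lesion-level model are not wrong in themselves either.

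A reader might also infer that "History of peripheral vascular disease" distorts the adjustment, since enrollment is of "Subjects with symptomatic PAD eligible for treatment". The item is undefined and could refer to earlier disease or intervention. If it is constant, it cannot be found unbalanced and never enters the model. It would be uninformative, not harmful.

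Finally, a reader might infer that the plan puts ABI and TBI on one scale. It only lists them together without a coding rule. Even if raw values were pooled with two all-TBI sites, adding that variable hardly moved the false site-signal rate: 15.5% without and 14.9% with it for 8 sites, 18.1% and 18.3% for 12, 20.2% and 18.9% for 18.

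**Conclusion.** The point holds as a low-cost improvement to a supportive analysis. The list in SAP 4.2 and Protocol 7.14 has no lesion descriptor, the endpoint is lesion-level, and RVD is a mechanical driver of success on the plan's own bit-size reasoning. If lesion mix differs between sites, a site p-value below 0.10 cannot be read as a site effect.

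The size is conditional. Under the assumed values, false signals rise from about 16% to between 19% and 51% as the difference in mix and its effect on success grow, with no change when mix is equal. These figures treat lesions as independent and use mixes and success rates that the documents do not supply. The RVD calculation assumes a channel equal to the bit diameter. The primary test against 76% is unaffected.

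**What to change.** In SAP 4.2 and Protocol 7.14, for the effectiveness endpoint:

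- Add core-laboratory RVD, vessel (SFA, popliteal, tibial), lesion length and total occlusion to the candidate covariates, and screen them for balance across sites.
- Enter them in the site model under the existing rule, that is, only when unbalanced. Do not force them all in, because only about 23 failures are expected.
- Leave out baseline stenosis, which overlaps with occlusion (an occlusion is 100% stenosis).
- State that raw ABI and TBI values are not pooled as one continuous variable. Analyse them separately, or rely on Rutherford category, which is already listed.

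The cost is a few lines of text, a few more balance tests and possibly one to three more model terms. The anatomy comes from imaging that the protocol already requires, so no new visits or data collection are needed.
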